### Sub-study 1: Acceptability

We will evaluate balance in key demographics, anthropometry, health history, and dietary history, using descriptive statistics, and will adjust for the covariates listed in Table 8 as fixed effects in the outcome models if they are strongly correlated with the primary outcome. Outcomes will be analyzed using the methods specified in Table 9.

*Table 8. Covariates to evaluate in the acceptability study*

Variables	Type of variable	Planned statistical analysis
Demographics		
Sex	Categorical (binary)	Descriptive count (%), covariate
Age (months)	Continuous	Descriptive means (SD) or medians (IQR), covariate
Mother age (years)	Continuous	Descriptive means (SD) or medians (IQR), covariate
Anthropometry		
Weight (kg)	Continuous	Descriptive means (SD) or medians (IQR), covariate
Height (cm)	Continuous	Descriptive means (SD) or medians (IQR), covariate
MUAC (mm)	Continuous	Descriptive means (SD) or medians (IQR), covariate
Health history		
Diagnosis of previous moderately acute malnutrition during the last 2 years	Categorical (binary)	Descriptive count (%), covariate
Experience of severe acute malnutrition during the last 2 years	Categorical (binary)	Descriptive count (%), covariate
Diagnosed illnesses during the last 3 months	Categorical (binary)	Descriptive count (%), covariate
Medication for a serious illness for the last 3 months	Categorical (binary)	Descriptive count (%), covariate
Dietary history		
Food consumption frequency (during the last month)	Count	Descriptive count (%), covariate
Breastfeeding status at inclusion (Exclusive)	Categorical (binary)	Descriptive count (%), covariate
Average number of breastfeeding sessions per day during the last month	Count	Descriptive count (%), covariate
Appetite test		
Observed dose intake/ consumed (g) (day 1)	Continuous	Descriptive means (SD) or medians (IQR), covariate

 The parameters are weekly monitored during the study, and any occurrence of health degradation (illness or progression to SAM) will result in withdrawal from the study.

Table 9. Statistical methods for each outcome in the acceptability study

	Type of variable	Planned statistical analysis
Primary outcomes		
Observed dose intake/ consumed (g) (after product trial for 7 days)	Continuous	Descriptive means (SD) or medians (IQR), analyzed with Linear Mixed Model (LMM) regressions with sequence and period as fixed effects
Secondary outcomes		
Product adaptation (difference ( $\Delta$ ) between observed dose intakes (g) on day 1 and after a one-week trial)	Continuous	Descriptive $\Delta$ means (SD) or $\Delta$ medians (95% CI), analyzed with repeated-measures LMM (compound symmetry covariance) with sequence and period as fixed effects
Reason for ending test dose (refusing the product)	Categorical	Descriptive count (%); analyzed with multinomial mixed model with sequence and period as fixed effects
Number of empty sachets returned (adherence indicator)	Count	Descriptive count (mean $\pm$ SD), analyzed with Poisson mixed model with sequence and period as fixed effects
Report on product sharing (adherence indicator)	Categorical (binary)	Descriptive count (%); chi-square test
Number of times per day the product was consumed at home (intake frequency)	Count	Descriptive count (mean $\pm$ SD), analyzed with Poisson mixed model with sequence and period as fixed effects
Perceived liking scores (by caretakers)	Ordinal (Likert scale)	Descriptive medians (IQR), analyzed with Poisson mixed model regressions with sequence and period as fixed effects
Product ranking/selection (by mothers)	Count	Descriptive count (%); analyzed with Poisson mixed model with sequence and period as fixed effects
Food frequency changes during each product trial	Count	Descriptive means (SD); analyzed with repeated-measures LMM with sequence and period as fixed effects or non-parametric Friedman test (if not normal)
Breastfeeding frequency during each product trial	Count	Descriptive count (mean $\pm$ SD); LMM or Poisson mixed model with sequence and period as fixed effects to assess differences between treatments

Adverse effect report (diarrhea, vomiting, and any others)	Count	Descriptive incidence rates; analyzed with Poisson mixed model with sequence and period as fixed effects
--	-------	--

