#### Sub-study 1: Acceptability

In a sub-set of facilities, we will conduct a 3x3 full Latin square crossover design to evaluate acceptability of the two products to address objective 1 (acceptability of S-RUTF and SMS-RUTF) and assess the adaptation to the products to address objective 2 (sensory adaptation). The 3x3 full Latin square crossover design will involve measurements of the RUSFs' observed intakes at four time points — baseline (day 1), day 8 (product switching), day 15 (product switching), and day 22.

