### Sub-study 1: Acceptability

The primary and secondary outcomes for the acceptability study and their definitions are listed in Table 2.

*Table 2. Primary and secondary acceptability outcomes*

Outcome type	Outcome definition
Primary	Observed dose intake/ consumed (g) after one week trial
Secondary	Adaptation effect (difference between observed dose intakes on first day and after one week trial)
Secondary	Reason for ending test dose (refusing the product)
Secondary	Proportion of empty sachets returned relative to the number of sachets received one week before (adherence indicator)
Secondary	Caregiver-reported product sharing (binary adherence indicator)
Secondary	Caregiver-reported number of times per day the product was consumed at home (intake frequency)
Secondary	Perceived liking scores (by caretakers) according to Likert scale
Secondary	Product ranking/selection (by mothers)

Secondary	Food frequency changes during each product trial
Secondary	Breastfeeding frequency during each product trial
Secondary	Caregiver-reported presence of an adverse effect (diarrhea, vomiting...)

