### Sub-study 1: Acceptability

A total sample size of 102 children was targeted based on recommendations in UNICEF protocols for acceptability testing of novel RUTF products, the requirement for complete sequences in a 3×3 full Latin square crossover design, and statistical power considerations. The sample size is consistent with the statistical power considerations, assuming a non-inferiority margin of 4 grams per observed intake in 30 minutes from a test dose, a between-subject standard deviation (SD) of 6.75 grams per kilogram body weight from literature, a conservative intra-class correlation (ICC) of 0.3, and an overall alpha (two-sided) of 0.05 (translating to a one-sided alpha of 0.025 for a non-inferiority test), 90% power, and attrition rate of 20%.

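### SAP Table 9 tests product sharing in the crossover with a chi-square test for independent samples, which is conservative when a child's reports are positively correlated

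*SAP*

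**What the plan says.** SAP, Study design, Sub-study 1 sets up a "3x3 full Latin square crossover design", with intake observed at "baseline (day 1), day 8 (product switching), day 15 (product switching), and day 22". Each child therefore spends one week on each of the three products. SAP Table 2 lists caregiver-reported sharing as a binary secondary outcome and an adherence indicator.

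In SAP Table 9 the whole analysis entry for sharing is "Descriptive count (%); chi-square test". Every other outcome in that table gets a within-child method:

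- The reason for stopping the test dose, the closest categorical outcome, gets a multinomial mixed model with sequence and period.
- Returned empty sachets, the other adherence indicator labelled as such, get a Poisson mixed model with the same terms.
- Food frequency gets a repeated-measures mixed model, or a Friedman test if the data are not normal. The Friedman test respects the pairing but adjusts for neither period nor sequence.

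The sample-size section for the sub-study states that "A total sample size of 102 children was targeted", with an "attrition rate of 20" per cent, and assumes "a conservative intra-class correlation (ICC) of 0.3" for intake. No sharing rate, and no correlation for sharing, appears anywhere.

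**The concern.** A Pearson chi-square on sharing by product assumes that all reports are independent. In a crossover the same caregiver and child supply the reports for all three products, and households that share one product are likely to share another. Comparing products within a child removes the between-household variation; the Pearson statistic leaves it in the error term. The test is then less sensitive than the design allows, and it also leaves out any drift in sharing over the three weeks.

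The direction matters because the SAP's hypothesis for the sub-study is that the products have similar acceptability. A test that leans towards no difference leans towards that conclusion.

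**Working it through.** **No figure to reproduce.** The SAP states no error rate or power for sharing.

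**Inputs from the SAP.** 102 children and 20% attrition: 102 × 0.80 = 81.6, taken as 82 (81 in the last step below). Three products per child. Nominal two-sided alpha 0.05.

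**Assumed inputs.** Sharing of 30% on all products for type I error; 20/30/40% for power; latent within-child correlation from 0 to 0.7. The SAP's only correlation, 0.3, is for intake.

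**Analytic type I error.** Let ρ be the correlation between two binary reports from one child, with equal sharing rates. The variance of a difference between two products is 2p(1−p)(1−ρ)/n. The Pearson test uses 2p(1−p)/n. So the 3×2 Pearson statistic is distributed as (1−ρ) times a chi-square on 2 df, and

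true alpha = P(χ²₂ > 5.991/(1−ρ)) = 0.05^(1/(1−ρ)).

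- ρ = 0: 0.050
- ρ = 0.1: 0.05^1.111 = 0.036
- ρ = 0.2: 0.05^1.25 = 0.024
- ρ = 0.3: 0.05^1.429 = 0.014
- ρ = 0.5: 0.05^2 = 0.0025

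For a pairwise 2×2 comparison the formula is P(χ²₁ > 3.841/(1−ρ)), which gives 0.039, 0.028, 0.019 and 0.0056 at ρ = 0.1, 0.2, 0.3 and 0.5.

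**Simulation.** 82 children, probit random intercept, 20,000 replicates per setting. Correlation here is on the latent scale, which exceeds the binary ρ: at 30% sharing, latent 0.3 corresponds to a binary ρ of about 0.18, and latent 0.7 to about 0.48.

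| Latent correlation | Chi-square type I error (30% throughout) | Chi-square power (20/30/40%) | Cochran's Q power (20/30/40%) |
|---|---|---|---|
| 0 | 4.9% | 71% | 71% |
| 0.1 | 4.1% | 72% | 74% |
| 0.2 | 3.3% | 72% | 77% |
| 0.3 | 2.8% | 72% | 80% |
| 0.5 | 1.2% | 72% | 87% |
| 0.7 | 0.3% | 73% | 94% |

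Cochran's Q keeps its type I error at 4.9 to 5.2% throughout. Repeat runs differ by a point or two in power and put type I error at latent 0.7 between 0.3% and 0.4%. The formula agrees: latent 0.3 gives 0.05^(1/0.818) = 0.026.

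**A second alternative.** 81 completers, sharing of 30/30/15%, correlation on the binary scale. Chi-square against Cochran's Q: 63.5% and 63.0% at ρ = 0; 65% and 70% at 0.1; 63% and 79% at 0.3; 63% and 91% at 0.5.

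No period effect was simulated, so these figures measure only the cost of ignoring the pairing.

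**The case against.** Much can be said on the other side.

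- *The inputs are assumed.* This stands. At zero correlation nothing is lost, and at latent 0.1 to 0.2 the loss is about 2 to 5 points of power. Rarer sharing also shrinks the distortion: at 5% sharing and latent 0.3, type I error is 3.7%. A reader might take the gap of about 20 points as the expected loss, but that needs a latent correlation of 0.7, which nothing in the documents supports.
- *Per-product recording is inferred.* This stands as a caveat. The SAP says outright that food and breastfeeding frequency are taken for each product trial, but does not say so for sharing. The weekly switches make it the natural reading.
- *The term could loosely mean McNemar's test or Cochran's Q.* Nothing says so, and the cell would then still need clarifying.
- *A reader might infer false claims of a product difference.* The documents do not support that. With positive correlation the test rejects too rarely; only negative correlation, implausible within a household, would reverse this.
- *A reader might carry the point over to adherence in the main trial.* That does not follow. The SAP's Analysis frame section defines main-trial adherence by attendance at treatment visits, so sharing does not enter the complier analysis.

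**Conclusion.** The concern holds in a limited form. As written, Table 9 applies an independent-samples test to what are almost certainly repeated reports from the same child, and it is the only row without a within-child method. The result is a conservative test and a loss of power that ranges from nothing at zero correlation to about 8 points at latent 0.3 and about 21 at 0.7, under the 20/30/40% alternative. These sizes depend on assumed sharing rates and correlations, and on one report per product from about 82 children. The practical weight is small: sharing is one of ten secondary outcomes in the acceptability sub-study.

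**What to change.** Replace the Table 9 entry for sharing with a logistic mixed model containing product, period and sequence and a random child effect, or a GEE logistic model with the same terms clustered on the child. This matches the mixed-model rows and can use children who miss a period. State in Tables 2 and 9 that sharing is recorded for each product week.

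Cochran's Q, with McNemar's test for pairs, can serve as a simpler fallback if the model does not converge. It should not be described as equivalent: it adjusts for neither period nor sequence, and it needs all three reports from each child, while 20% attrition is expected.

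The cost is one table cell and a clarifying phrase. If sharing is collected weekly, as the design implies, no new data, visits or sample size are needed.

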- **Alternative, soy-based RUTF (S-RUTF) formulation (intervention 2):** a milk- and peanut-free product with added crystalline amino acids

Burkina Faso national guidelines for MAM and SAM treatment will be followed for dosing the products and all other aspects of treatment (Table 1 and

Table 2). Thus, all children will receive the standard of care for CMAM treatment in Burkina Faso, with the only difference between treatment arms being the product received. Burkina Faso national guidelines for CMAM are detailed in the guideline document (12). Briefly, upon admission to treatment for SAM, children will undergo medical evaluation and receive routine antibiotics and rapid diagnostic test for malaria as well as other treatment as indicated in the guidelines. The caregiver of the child will be provided with RUTF and instructed on how to use it. Children will be followed weekly at the health center to be re-evaluated. At the follow-up visits, children's anthropometry will be measured, a clinical examination will be performed, and the caregiver will be provided with another 7-days' supply of RUTF with instructions. Children will be treated a maximum of 12 weeks and will be eligible to be discharged when they have achieved anthropometric recovery (defined in Table 3). For MAM, upon admission to treatment, children will be provided with RUTF to be used as a food supplement in addition to the child's usual diet. Caregivers will be provided with the product and instructed on its use, and receive nutritional counseling as per guidelines. Children will receive medical treatments as indicated in the guidelines, and instructed to return to the health facility every two weeks for monitoring. Children will be treated for a maximum of 12 weeks and be eligible for discharge when they have achieved anthropometric recovery.

Table 1. Burkina Faso guidelines for dosage for MAM (12)

Sachets per day (92 gram sachets)	Sachets per week (92 gram sachets)	Sachets per two weeks (92 gram sachets)
1	7	14

Table 2. Burkina Faso guidelines for dosage for SAM (12)

Child's weight (kilograms)	RUTF - grams		RUTF – sachets (92 grams)	
	Grams per day	Grams per week	Sachets per day	Sachets per week
3.0-3.4	105	750	1 ¼	8
3.5 – 4.9	130	900	1 ½	10
5.0 – 6.9	200	1400	2	15
7.0 – 9.9	260	1800	3	20
10.0 – 14.9	400	2800	4	30
15.0 – 19.9	450	3200	5	35
20.0 – 29.9*	500	3500	6	40

Storage of product

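### SAP Table 9 analyses the ordinal liking score with a Poisson mixed model whose assumed variance is too large, so its standard errors are too wide and small to moderate differences between products are missed

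*SAP*

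**What the plan says.** The acceptability sub-study is a crossover (SAP, Study design, Sub-study 1): "we will conduct a 3x3 full Latin square crossover design to evaluate acceptability of the two products". The SAP's sample size section targets 102 children and allows 20% attrition. SAP Table 2 lists the secondary outcomes and Table 9 assigns a method to each. Three rows matter here.

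- **Liking.** Table 2: "Perceived liking scores (by caretakers) according to Likert scale". The number of scale points is not given. Table 9 types it as ordinal and plans: "Descriptive medians (IQR), analyzed with Poisson mixed model regressions with sequence and period as fixed effects".
- **Sachets.** Table 2 defines "Proportion of empty sachets returned relative to the number of sachets received one week before (adherence indicator". Table 9 instead models "Number of empty sachets returned (adherence indicator" as a count in a Poisson mixed model, with no denominator or offset.
- **Ranking.** Table 9 lists "Product ranking/selection (by mothers", types it as a count and plans: "Descriptive count (%); analyzed with Poisson mixed model with sequence and period as fixed effects".

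None of the three rows names a dispersion parameter, a robust variance or an alternative model, and none lists product among the fixed effects. The primary outcome, observed intake, has a linear mixed model. The sub-study hypothesis is that each new product is similar in acceptability to standard RUTF.

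**The concern.** Poisson regression takes its standard errors from the assumption that variance equals mean. A Likert score is bounded at both ends and, for a well-liked food, varies much less than that. A mixed model offers no escape: a random intercept can add variance but cannot remove it. If the model-based standard errors are used, the confidence intervals for liking are too wide and the test is far below its nominal size. A modest but real difference in how caregivers rate the products could then go unreported. Ranks and sachet counts are bounded too, so the same question arises there.

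**Working it through.** **Inputs.** From the SAP: 102 children, 20% attrition, three products each tried by every child, and an intra-class correlation of 0.3 (stated for intake, borrowed here for liking). Completers: 102 × 0.8 = 81.6, taken as 81. From Protocol Table 1, column "Sachets per week (92 gram sachets": 7 for MAM children, the only group this sub-study recruits, so the weekly sachet count runs from 0 to 7. Assumed, because the documents do not say: the number of Likert points, the score distributions, the sachet return patterns and model-based standard errors.

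The SAP states no power or variance for these three outcomes, so there is no figure of its own to reproduce. The 102 relates to intake and is used only to obtain the completers.

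**Liking: the bound.** For a score on 1-5 with mean m, the largest possible variance is (5 − m)(m − 1). It is below m when m² − 5m + 5 > 0, that is when m > (5 + √5)/2 = 3.62. Above that mean the Poisson variance is too large for every possible distribution.

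**Liking: hand check at mean 3.9, variance 0.98.**
- Poisson standard error of a difference between two products: √(2 × 3.9 / 81) = 0.310. Significance needs 1.96 × 0.310 = 0.61 points.
- Actual standard error with within-child correlation 0.3: √(2 × 0.98 × 0.7 / 81) = 0.130. Significance should need 1.96 × 0.130 = 0.26 points.

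**Liking: simulation.** Six sequences, three periods, 81 completers; fixed effects for product, period and sequence; two-sided 5% level; compared with a paired test on the same data. Where two values appear, they come from two simulations with slightly different score distributions (variance 0.98 and 0.88) and true differences (about 0.3 and 0.33; 0.5 and 0.51).

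| 5-point scale, mean about 3.9 | Poisson | Paired test |
|---|---|---|
| No difference | 0% | 4-5% |
| About 0.3 points | 1-2% | 52-68% |
| About 0.5 points | 29-30% | 92-95% |
| About 0.8 points | 96% | 100% |

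Other scales under no difference: 5-point with mean 3.0 and variance 1.29, 0.2% against 6.5%; 9-point with mean 7.2 and variance 2.9, 0.0% against 4.8%. The random-intercept variance was estimated at zero in every 5-point run and in 90-100% of the 9-point runs.

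**Ranking.** For ranks 1-3 with no preference, each rank has variance 2/3 and two ranks from one mother have covariance −1/3. The difference therefore has variance 2/3 + 2/3 + 2/3 = 2, while Poisson assumes 2 + 2 = 4. The standard error is √2 too large and the true size is P(|Z| > 1.96 × √2) = 0.56% (simulated 0.5%). With a simulated preference (Gumbel utility shift 0.5), power is 32% against 64%. If instead the analysis counts how often each product is chosen first, the difference has variance 1/3 + 1/3 = 2/3 under both the multinomial and the Poisson model. Size is then correct (4.5% against 4.5%) and power equal (41% against 41%).

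**Sachets.** On 0-7 the largest variance is m(7 − m), which is certain to be below m only if m > 6.

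| Return pattern (assumed) | Variance / mean | Poisson, no difference | Paired test |
|---|---|---|---|
| Near-complete, binomial-like, 90% | 0.6-1.25 / 6.3 | 0% | 4-5% |
| 15% of visits return none | 5.8 / 5.7 | 7.0% | 5.2% |
| All or none, 80% return | 7.9 / 5.6 | 9.2% | 5.8% |

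With near-complete returns, power for a 10% drop is 19-24% against 91-100%; a 20% drop is found 99-100% of the time.

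**The case against.** A reader might infer three stronger things, and the documents support none of them.

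1. *The tests cannot reject, whatever caregivers report.* Not so. Differences of about 0.8 points are detected 96% of the time, and large sachet drops and strong rank preferences are also found. The loss is confined to small and moderate differences.
2. *The plan is tilted towards declaring similar acceptability.* The hypothesis is worded that way, but the SAP nowhere says that a non-significant secondary test will be read as similarity. Its only acceptability margin, 4 g, applies to intake. Judged by a margin, over-wide intervals would make similarity harder to claim.
3. *All three outcomes share the fault.* The sachet error depends on an unknown return pattern and can turn slightly liberal. Table 9's count type and count (%) summary for ranking also fit first-choice counts, for which the Poisson test is sound.

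Three further points are fair. Medians, means and counts will be reported as well, so caregivers' answers stay visible. With a fixed 7 sachets a week, the count and the proportion differ only by a scale factor, so the Table 2 and Table 9 mismatch is mainly one of wording. Robust standard errors would remove most of the liking problem; the SAP names them for Poisson models, but only for binary outcomes in the main trial, not in Table 9.

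What stands is the liking row: an outcome labelled ordinal is given a count model with the wrong variance.

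**Conclusion.** The point holds for liking. Followed as written with model-based standard errors, Table 9 gives a test with a true size of about 0% and intervals more than twice as wide as they should be (0.310 / 0.130 = 2.4) at a mean near 3.9. For differences of 0.3 to 0.5 points most of the power is lost. The direction is certain on a 1-5 scale once the mean exceeds 3.62. The size rests on the assumed distributions, but the null rejection rate was 0.2% or less on every scale tried.

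For ranking the point is conditional on raw ranks being modelled. For sachets it is that the test's size is unknown, between about 0% and 9% in the patterns tried. These are secondary outcomes of a nested sub-study. The intake analysis and the main trial do not depend on them.

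**What to change.** Amend Table 9 as follows.

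- **Liking:** a cumulative-logit mixed model with a child random effect. The linear mixed model already used for intake is acceptable; robust standard errors are the minimum. State the number of scale points.
- **Sachets:** a binomial or beta-binomial mixed model of sachets returned out of sachets received, so that Table 9 matches the proportion defined in Table 2.
- **Ranking:** state whether full ranks or first choices are analysed. If ranks, use a Friedman test or a rank-ordered logit.
- **All regression models:** name product as a fixed effect alongside sequence and period. For all three outcomes, report product differences with confidence intervals.

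The cost is SAP wording only. The data collected do not change and the methods are in standard software.
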